## **Rationale and background**

Fabry disease is a rare X-linked lysosomal disorder in lysosomes, resulting in a multisystemic disorder caused by deficiency in the enzyme  $\alpha$ -galactosidase A ( $\alpha$ -Gal A) due to mutations in the GLA gene, encoding the hydrolase  $\alpha$ -Gal A enzyme, which catalyses glycosphingolipids namely globotriaosylceramide (Gb3). Reduced or absent  $\alpha$ -Gal A activity leads to accumulation of Gb3 in the lysosomes of various organs, as well as cellular dysfunction and inflammation causing physical symptoms and eventual organ failure (1,2). Fabry disease as an X-linked disorder with a high penetrance, though not 100% in female heterozygotes, although the disease affects both males and females. With the X-linked nature, Fabry disease is suitable for an efficient, high diagnostic yield cascade screening over at least three generations surrounding an index-patient. The Danish National Fabry Centre has now more than 20 years of experience of cascade screening, which has provided a patient population of 115 male and female patients. The prevalence of Fabry disease in the Danish population is estimated to be 1:58000 (males 1:85000, females 1:44000) (3).

Primarily male patients, with early onset classical phenotypes have none or very low  $\alpha$ -Gal A activity, and they inevitably develop multiorgan failure without treatment (4). Patients with late onset of Fabry disease represent both males and females with higher  $\alpha$ -Gal A activity and variable degrees of organ involvement (5). Fabry disease can cause irreversible damage to multiple organs resulting in Fabry associated clinical events (FACEs) such as renal, cardiac, cerebrovascular events, and death (5).

The primary Fabry specific therapy has historically been enzyme replacement therapy (ERT), and as of 2016 an oral chaperone therapy, Migalastat, has been available, providing an alternative to ERT for patients with amenable mutations by increasing their endogenous  $\alpha$ -Gal A enzyme activity (6–14). However, real-world long-term data from well-characterised cohorts with available detailed clinical consecutive observations with focus on treatment with Migalastat and Fabry associated events has not been fully investigated (12–14).

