2. OVERVIEW OF STUDY DESIGN

This is a retrospective study of prospectively collected patient data with the use of secondary patient data from both paper and electronic patient files. All patients are treatment naïve at time of diagnosis. Both migalastat and ERT will be studied retrospectively. Also untreated patients will be studied by assessment of relevant clinical and laboratory variables. The analysis will originate at the time of diagnosis.

The patients have been followed for more than 20 years from 2001 until December 2023. All identified patients with Fabry disease, whether receiving specific Fabry medication or not, have been offered annual or biannual thorough workups including examinations of Fabry associated organ function and symptoms. The study will be carried out at the Danish National Fabry Centre, Department of Endocrinology, Copenhagen University Hospital.

All patients from the Danish National Fabry Centre will be included. Subgrouping is aimed at depending on available numbers: non-amenable, amenable, classic, non-classic, males, females, treated including type of treatment or untreated.

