5. DEFINITION OF PATIENT POPULATIONS TO BE ANALYZED

5.1. Safety Population

The Safety Population will include all patients with Fabry disease who consented to participate and enrolled in the study. Patient disposition and reason for discontinuations will be presented in the Safety Population.

Patients who enter the study as untreated but switch to a treatment (migalastat or ERT) within 3 months from enrollment will be considered in analysis as initially belonging to a treatment group they switched to. Depending on an analysis as further discussed the group assignment might change in the case of a treatment switch.

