5.2. Effectiveness Populations

5.2.1. Primary Effectiveness Population

The Primary-Effectiveness Population is defined as subsets of the migalastat-treated group, the untreated group, and ERT-treated group as comparators.

Patients who enter the study as untreated but switch to a treatment (migalastat or ERT) within 3 months from enrollment will be considered in analysis as initially belonging to a treatment group they switched to. Depending on an analysis as further discussed the group assignment might change in the case of a treatment switch.

All data collected will be utilized to establish the Primary Effectiveness Population for the analysis. Patients need to have a documented amenable variant to be included in the Primary Effectiveness Population and must meet criteria for receiving treatment for migalastat.

All patients from the Danish National Fabry Centre will be included, estimating the inclusion of 115 individuals (sex ratio [female:male] – 2:1). Pre-specified subgroups include: non-amenable/ amenable to migalastat, males/females.

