Prior to imputation of dates, the percentage of patients with completely missing start of therapy date, and separately with missing month will be calculated and presented in a table overall and by treatment group at enrollment.

Similarly, the percentage of patients with completely missing end of therapy date, and separately with missing month will be calculated and presented in a table overall and by treatment group at enrollment.

At least the year needs to be present to determine if the patients are eligible for inclusion in the Primary and Secondary Effectiveness Populations.

The following rules apply to the start date:

- If year is present and month and day are missing: set month and day to 1 July.
- If year and day are present and month is missing: set month to July.
- If year and month are present and day is missing: set day to the 15th of the month.

The following rules apply to the end date:

- If the end date is completely missing and the patient did not switch therapy, then the end date is imputed as the discontinuation date.
- If the end date is completely missing and the patient switched therapy, then the end date is imputed as the therapy switch date.
- If year is present and different from the year of the start date, and month and day are missing: set month and day to 1 July.
- If year is present and the same as the year of the start date, and month and day are missing: set month and day to 31 December.
- If year and day are present and month is missing: set month to July.
- If year and month are present and day is missing: set day to the 15th of the month.

Any partial dates will be displayed in data listings without and with imputation of missing days and/or months.

Treatment Switch

Prior to imputation of dates, the percentage of patients with completely missing switch of therapy date, and separately, the percentage of patients with missing month will be calculated and presented in a single table overall, and by treatment group at enrollment. Patients can change therapy more than once during the 20-year period. The percentages of patients with any completely missing switch of therapy dates or any missing therapy switch month will be presented. Additionally, a table with percentages of missing switch dates by group a patient switched to (migalastat-treated, ERT, untreated) will be presented.

The following rules apply to start date of new or switched therapy:

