- If start date is completely missing: start date will be imputed as 30 days past enrollment date.

- If (year is present and month and day are missing) or (year and day are present and month is missing): set month and day to the date of the first closest visit, unless another switch occurred before it. In such a case, set the start date to the date of the previous visit.
- If year and month are present and day is missing: set day to the first day of the month unless during that month there was a visit, in which case the day will be set to the day of that visit.

The following rules apply to end date of new or switched therapy:

- If end date is completely missing: end date will not be imputed unless there is another treatment switch. In that case, the end date is imputed as a day before that next treatment switch.
- If (year is present and month and day are missing) or (year and day are present and month is missing): set month and day to the date of the last visit in that year, unless another switch occurred. In such a case, set the end date to a day before that next treatment switch.
- If year and month are present and day is missing: set day to the date of the last day of the month.

Any partial dates will be displayed in data listings without and with imputation of missing days and/or months.

Concomitant Medications

The following rules apply to start date:

- If start date is completely missing: start date will not be imputed.
- If (year is present and month and day are missing) or (year and day are present and month is missing): set month and day to 1 January.
- If year and month are present and day is missing: set day to first day of the month.

The following rules apply to end date:

- If end date is completely missing: end date will not be imputed.
- If (year is present and month and day are missing) or (year and day are present and month is missing): set month and day to 31 December.
- If year and month are present and day is missing: set day to last day of the month.

Any partial dates will be displayed in data listings without imputation of missing days and/or months (eg, MAR2011, 2009). No other imputation of missing data will be performed.

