11. DEFINITION OF STUDY TIME POINTS

11.1. Definition of Diagnosis Date

Enrollment is the date on which the patient was diagnosed with the Fabry disease. For analysis of assessments which were not collected on the diagnosis date, the assessment closest to the diagnosis date will be utilized. If there are 2 assessments that are equidistant from the diagnosis date, then the assessment prior to diagnosis will be utilized.

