15.5. Extent of Study Drug Exposure

Study treatment exposure will be summarized using the Safety Population.

Analyses for the extent of exposure will focus on the duration of each respective treatment (migalastat, ERT, or untreated). Duration will be defined as:

$$Dur = End\ date\ of\ treatment - start\ date\ of\ treatment + 1$$

Breaks in therapy or discontinuation in exposure as well as switching therapy will be accounted in the calculations. Missing dates will be imputed as described in Section 6.1. Exposure will be calculated after the dates are imputed.

Extent of exposure (in days) will be compared between the treatment groups using the Wilcoxon Rank Sum test. In addition, the number of patients treated at each visit will be presented by treatment group.

Other summaries which will be presented are average dose (mg) per time period (3 months), ongoing status (yes, no, unknown) and primary reason for interruption/discontinuation (adverse drug reaction, lack of efficacy, disease improvement, patient/guardian decision, investigator decision, pregnancy and/or breast feeding).

All exposure parameters will be included in a by-patient listing.

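### A therapy start with no recorded date is set to diagnosis + 30 days without any bound, which can credit migalastat with years before it was available, invert the order of drugs and change the initial treatment cohort

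*SAP*

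**What the plan says.** SAP 6.1, under Treatment Switch, covers the start of a new or switched therapy: "If start date is completely missing: start date will be imputed as 30 days past enrollment date". SAP 11.1 fixes the reference date: "Enrollment is the date on which the patient was diagnosed with the Fabry disease". SAP section 2 adds: "All patients are treatment naïve at time of diagnosis". Every migalastat or ERT start therefore comes after enrollment and falls under this rule when its date is wholly absent.

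Three other provisions act on the imputed date.

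- **Cohort.** Under SAP 5.1 and 5.2.1, patients who enter untreated but move to a drug "within 3 months from enrollment will be considered in analysis as initially belonging to a treatment group they switched to". SAP 3.1 bases the formal analysis on the initial treatment cohort.
- **Exposure.** SAP 15.5: "Exposure will be calculated after the dates are imputed". SAE incidence (15.3) uses that exposure. The time-dependent survival model (15.4) depends on the same treatment dates.
- **End date.** In 6.1, a completely missing end of a switched therapy stays open unless another switch follows; it then becomes the day before that switch.

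On timing, the protocol background states that "as of 2016 an oral chaperone therapy, Migalastat, has been available", and its Method section starts follow-up on 1 January 2001.

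Elsewhere in 6.1, under therapy prior to enrollment, stands a possible safeguard: "At least the year needs to be present to determine if the patients are eligible for inclusion in the Primary and Secondary Effectiveness Populations".

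**The concern.** The rule uses one fixed date for any drug and any calendar year. It ignores when the drug became available, what the visits show, and whether another therapy was already running. The neighbouring rules take more care: a partial switch date is tied to a visit and checked for an intervening switch, and a wholly missing concomitant-medication start is not imputed at all.

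Untreated or ERT time, with any events in it, can thus be booked to migalastat, the drug on which the study focuses. Person-time denominators, cohort membership and the intervals in the time-dependent models then become wrong. In the migalastat-versus-ERT comparison, where treatment start is the time origin, age, eGFR and LVMi would also be read at the wrong time.

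**Working it through.** The documents give no figure to reproduce: no count of migalastat patients, no frequency of missing dates and no event rate. The check is date arithmetic with the SAP 7.2 conversions (days/365.25 for years, days/30.4 for months).

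**Step 1. Is the imputed date always inside the 3-month window?** 30/30.4 = 0.99 months. The window is 3 × 30.4 = 91 days. Yes, always.

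**Step 2. Migalastat time before 2016, with no dated therapy in between.** Formula: (1 January 2016 − [diagnosis + 30 days])/365.25. The protocol gives only the year, so the last column uses 31 December 2016.

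| Diagnosis | Imputed start | Years to 1 Jan 2016 | Years to 31 Dec 2016 |
|---|---|---|---|
| 1 Jan 2001 | 31 Jan 2001 | 14.9 | 15.9 |
| 1 Jan 2003 | 31 Jan 2003 | 4718/365.25 = 12.9 | 13.9 |
| 1 Jan 2005 | 31 Jan 2005 | 10.9 | 11.9 |
| 1 Jan 2010 | 31 Jan 2010 | 5.9 | 6.9 |
| 1 Jan 2015 | 31 Jan 2015 | 0.9 | 1.9 |

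For comparison, time from 1 January 2016 to the end of follow-up is 7.0 years under the protocol (December 2022) and 8.0 years under the SAP (December 2023). The rule can give a patient diagnosed on 1 January 2001 21.9 or 22.9 years.

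**Step 3. ERT first, then migalastat with no start date.** This case works differently. Assume diagnosis on 1 January 2003, a dated ERT start on 1 January 2006, and no migalastat start or end date. Migalastat is imputed to begin on 31 January 2003. Because the ERT start is now the next switch, it ends on 31 December 2005. By the SAP 15.5 formula that is 1065 + 1 = 1066 days, or 2.9 years. All of it precedes the ERT that in fact came first, and the true migalastat period disappears. The 12.9 years of step 2 do not apply here. If a migalastat end date is recorded, the imputed interval overlaps the ERT interval instead.

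**Step 4. Scale, on assumptions only.** Assume 10 to 40 migalastat patients with a mean of 4 true years each, so 40 to 160 person-years. One patient of the step 2 kind adds:

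- 12.9 years: 12.9/40 = 32%, 12.9/80 = 16%, 12.9/160 = 8%
- 14.9 years: 14.9/40 = 37%, 14.9/80 = 19%, 14.9/160 = 9%

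**Step 5. Which populations?**

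| Reading of the year requirement in 6.1 | Effectiveness Populations | Safety Population |
|---|---|---|
| Covers only therapy before enrollment, as placed | Affected | Affected |
| Also covers switch dates | Patient excluded; the + 30 days rule contradicts it there | Affected |

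**The case against.** The strongest counter-argument is the year requirement. Its subsection speaks of ongoing therapy in the migalastat and ERT groups. Since all patients are treatment naïve at diagnosis, a strictly pre-enrollment reading leaves it little to govern. If it was meant to cover switch dates, a patient without even a year leaves both Effectiveness Populations and the primary analysis is protected. This stands as a possible reading. It does not rescue the text: 6.1 would then hold two incompatible rules, and the Safety Population would still use the imputed date.

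Second, the rule applies only when even the year is unknown. The protocol asks for a dated treatment record, visits yearly or every other year, a completeness check and a 10% second review. The SAP will tabulate missing switch dates before imputation. Such cases may be few, and they would be visible. That limits the likely size but does not make the rule correct, and no sensitivity analysis covers it.

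Third, SAP 11.2 already starts the clock at diagnosis for migalastat versus untreated, so pre-treatment years enter the migalastat arm even with perfect dates. For patients who belong in that arm anyway, this bias comes mainly from 11.2. What the imputation adds there is a change in who belongs to the arm.

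A reader might also infer more than the documents support:

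- *That the exposure predates the drug's existence.* The protocol gives 2016 as the year of approval and availability and refers to initial trials of migalastat. Earlier trial use by a Danish patient is neither stated nor excluded.
- *That true exposure cannot exceed 7 years.* The SAP's December 2023 cut-off gives 8, and trial use could give more.
- *That every affected patient moves out of the untreated group.* A patient with ERT dated within 3 months of diagnosis is already in the ERT cohort.
- *That ERT starts are also impossible.* No ERT availability date is given. For ERT, only the misplaced start and the cohort shift apply.

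The protocol's Study workflow section places study entry at the first visit to the centre. With that reference date the same problem arises 30 days after that visit.

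**Conclusion.** The point holds. As written, the rule can place migalastat about 12.9 years before 2016 for a diagnosis on 1 January 2003 and 14.9 years for 1 January 2001, provided no dated therapy lies in between and there was no earlier trial use. Where ERT came first, it normally inverts the sequence; if the migalastat end date is also missing, true migalastat time is lost. A patient with no other treatment dated in the first 3 months is moved into the initial treatment cohort of the drug with the missing date.

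Safety Population exposure, SAE rates and the time-dependent survival model are affected on any reading. Harm to the primary comparison depends on the year requirement not extending to switch dates, which the SAP leaves unclear. The number of affected patients is unknown. The 8% to 37% range for added person-years rests on assumed group sizes and is illustrative only.

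**What to change.** In SAP 6.1, delete the enrollment + 30 days rule and replace it as follows.

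1. Place an undated start between the last visit documented off the drug and the first visit documented on it, for example at the midpoint. With visits at most two years apart, the midpoint errs by no more than about one year.
2. Require the date to fall after the end of the preceding therapy and, for migalastat, not before 2016 unless earlier trial use is documented.
3. If no such bound exists, do not impute, and exclude the patient from the Effectiveness Populations. State explicitly that the year requirement applies to switch dates.
4. In 5.1 and 5.2.1, state that an imputed start date cannot trigger the 3-month reassignment.

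The cost is SAP wording and a small programming change. The downside is that a few patients without usable dates leave the effectiveness analysis.

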## **Research methods**

### **Study design**

Observational, retrospective, single-center study originating from the Danish National Fabry Centre, Centre of Cancer and Organ Disease, Department of Medical Endocrinology, Copenhagen University Hospital, Rigshospitalet. Patients are enrolled at the time of sampling leading to a genetically verified diagnosis of Fabry disease. Patients are followed from the day of enrolment until 31st of December 2022, having received yearly or bi-yearly evaluation during follow-up.

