13.1.2. Interval Based Cox Proportional Analysis for Fabry-associated Clinical Events

In the interval-based time to event analysis will be used with 3 time-dependent variables indicating whether or not a patient is on migalastat, ERT, or untreated at time t . A patient may be in 1 or more treatment groups and a patient may be both left and right censored. For example, a patient that begins migalastat, stops at Month 9, begins ERT at Month 24, and then dies at Month 26 will be represented 3 times in the design matrix; the first for migalastat being right censored at Month 9, the second being for ERT left censored at Month 24 and right censored at Month 26, and finally, for untreated, being right censored at Month 9 and having an event at Month 24.

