13.3. Secondary Endpoint: Incidence of FACEs

As this is an observational study, patients may switch or stop therapies. If a patient starts dialysis or receives a kidney or heart transplant, the events afterwards will be excluded.

The analysis of the incidence rate (number of patients with at least 1 event per 1000 person-years) will be performed on the Primary and Secondary Effectiveness Populations.

Treatment Switch

The analysis will address events that occur on migalastat or ERT therapy from the Analysis Start Date or switch date up until 30 days after the patient stops therapy or switches therapy. For the patients untreated at enrollment to the study, the analysis will address events from the time of diagnosis until the patient starts a therapy or during periods that they are untreated after a switch.

The second analysis will address events that occur on migalastat or ERT therapy from the Analysis Start Date or switch date. For the patients untreated at enrollment to the study, the analysis will address events from the time of diagnosis until the patient starts a therapy or during periods that they are untreated after a switch.

Analysis Methods

The calculation of the incidence rate (number of events per 1000 person-years) will be performed on the Primary and Secondary Effectiveness Populations.

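### As worded, the SAP 6.1 rules for year-only dates of new or switched therapy can override the recorded year, so untreated time may be counted as drug exposure

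*SAP*

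**What the plan says.** The rules are in SAP 6.1, under Treatment Switch, for start and end dates of new or switched therapy.

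- **End date, month missing:** "set month and day to the date of the last visit in that year, unless another switch occurred". The exception in full reads: "unless another switch occurred. In such a case, set the end date to a day before that next treatment switch".
- **End date, wholly missing, with a later switch:** "In that case, the end date is imputed as a day before that next treatment switch".
- **Start date, month missing:** month and day come from the closest visit, unless another switch came before that visit. "In such a case, set the start date to the date of the previous visit".

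The same section says that what is imputed is missing days and months. Its rules for therapy before enrollment keep a recorded year (1 July or 31 December), and so do its concomitant-medication rules.

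The SAP expects drug-free gaps. Its example patient in 13.1.2 "stops at Month 9, begins ERT at Month 24", and the incidence analysis in 13.3 counts events for the untreated group "during periods that they are untreated after a switch". The Protocol (Study design) describes patients as "having received yearly or bi-yearly evaluation during follow-up"; its Method section makes clear that this means every year or every other year.

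**The concern.** Both exceptions set a whole date, not only a month and day, and neither is tied to the recorded year. A stop recorded in one year can therefore be moved to the eve of a drug start several years later. A start can be moved back into a year before the one recorded. The default for stops also yields no date when a patient seen every other year had no visit in the stop year.

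These rules carry most of the load. Patients are treatment-naïve at diagnosis, and SAP 11.1 equates enrollment with diagnosis, so the year-preserving rules for therapy before enrollment have little to act on. Missing months are plausible in paper and electronic files going back to 2001, and the SAP plans to tabulate them.

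Imputed dates matter downstream. SAP 15.5 computes exposure after imputation, and the SAE rates in 15.3 use that exposure. Stop and switch dates set the on-therapy windows in 13.1.1 to 13.3, and 15.1 assigns SAEs to the group at the time of the event. No sensitivity analysis to the imputed dates is planned.

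**Working it through.** The documents give no figure to reproduce, so the check applies the rules literally. Months are days/30.4 and years are days/365.25, as in SAP 7.2.

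**1. Does a recorded year carry any information?**
- Stop wholly missing, later switch exists: end = next switch − 1 day.
- Stop year known, month missing, later switch exists: end = next switch − 1 day.

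The results are identical. Once there is a later switch, the recorded year has no effect.

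**2. The SAP's own patient (13.1.2).** Only the treatment dates of that example are used: migalastat from Month 0, stop at Month 9, ERT at Month 24. Suppose the stop is known by year only.
- Imputed end = the day before Month 24.
- Migalastat exposure: about 24 months instead of 9; 24/9 = 2.67 (2.64 to 2.67 when counted in days, depending on the starting month).
- Untreated gap: 24 − 9 = 15 months, reduced to none.
- Over all 12 possible starting months, the imputed end falls one or two calendar years after the recorded year. It lies 3.0 to 13.9 months past 31 December of that year. Shortest case: start 1 April 2017, stop 1 January 2018, ERT 1 April 2019, imputed end 31 March 2019; 90/30.4 = 3.0 months past 31 December 2018.
- An event at Month 14 is outside the true on-therapy window, which closes at 9 + 30/30.4 = Month 10.0. After imputation it counts as on migalastat.

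**3. Longer gaps (assumed dates).** Stop recorded as 2010, next switch on 1 June of the year shown:

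| Next switch | Imputed end | Years past 31 Dec 2010 |
|---|---|---|
| 2010 | 31 May 2010 | none; year kept |
| 2011 | 31 May 2011 | 0.41 |
| 2013 | 31 May 2013 | 2.41 |
| 2017 | 31 May 2017 | 6.41 |
| 2020 | 31 May 2020 | 9.42 |

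**4. Start dates (assumed dates).** Start recorded as 2012, another switch before the closest visit, previous visit on 1 November 2011 (yearly visits) or 1 November 2010 (every other year). The imputed start precedes the earliest date the record allows, 1 January 2012, by 61/365.25 = 0.17 or 426/365.25 = 1.17 years. If the true start lies before the visit that would otherwise be used, the shift cannot exceed the visit interval, 1 or 2 years.

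**5. Direction of bias (all inputs assumed).** Take 20 patients with 4 years each on drug: 80 person-years at 30 events per 1000, or 2.4 events. Let the off-drug rate be 60 per 1000.
- One patient with a 1.25-year gap: (2.4 + 0.075)/81.25 = 30.5 per 1000; person-years up 1.6%.
- Five patients with 6-year gaps: (2.4 + 1.8)/110 = 38.2 per 1000; person-years up 37.5%.
- If the gaps contain no events: 2.4/81.25 = 29.5 and 2.4/110 = 21.8 per 1000.

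The drug's rate can move either way.

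**The case against.** **A same-year switch was meant.** The exception follows directly on a reference to visits in the recorded year. The bullet begins by setting only month and day, and the section describes its scope as missing days and months. On that reading the exception merely stops a therapy overlapping the next one. This is a fair account of probable intent, but the words do not contain the limit, and a programmer who follows them would code the literal rule.

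**Breaks in therapy are accounted for.** SAP 15.5 says so for exposure. But it also computes exposure after imputation, so a gap already removed cannot be recovered.

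**Stopping may itself count as a switch.** SAP 6.1 lists untreated among the groups a patient can switch to. The next switch after a stop is then the start of the untreated period, and the gaps in steps 2 and 3 need not disappear. That stands as a limit on the examples. It does not make the rule usable: the end date would depend on the same partly dated event, and the programmer would have to fall back on the start rule.

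**The extent would be visible.** The SAP tabulates missing dates and months before imputation and lists partial dates with and without imputation. This helps detection but neither caps the error nor tests its effect.

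A reader might infer that off-drug years will certainly become drug exposure, that a sizeable number of person-years is involved, or that the primary hazard ratio is distorted in a known direction. The documents support none of these. They give no count of year-only stops, and the literal reading is not the only one. The formal primary comparison uses the initial treatment cohort, so the end-date rule reaches it only for migalastat patients who stop and later switch or restart. Migalastat became available in 2016, so long gaps that begin before then concern ERT.

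**Conclusion.** The point holds as a defect of wording with real consequences if coded literally. The end-date rule can override a recorded year whenever three conditions meet: a missing month, a drug-free gap, and a next switch in a later year. Direct drug-to-drug switches, same-year switches and dates with a known month are unaffected. For the SAP's own example, the cost is 15 months of untreated time counted as migalastat exposure. Over the assumed gaps, at least 0.41 to 9.42 years per patient would be misassigned. These sizes assume that stopping does not itself count as a switch.

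The start-date fault is smaller, bounded by the visit interval, and arises only when another switch precedes the closest visit. How many patients are affected cannot be known from the documents, and the direction of bias is not fixed. The analyses mainly exposed are the interval-based Cox model, incidence, prevalence, time to first event within each treatment period, exposure and SAEs. The text needs clarifying under any reading.

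**What to change.** In SAP 6.1, for start and end dates of new or switched therapy:

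1. State that an imputed date must stay within the recorded year.
2. Use the day before the next switch as the end date only if that switch falls in the same recorded year. Say whether stopping therapy counts as a switch for this rule.
3. Give a within-year default when there is no usable visit in the recorded year. One option is 1 July, as the section already uses for therapy before enrollment, kept between the therapy start and the next switch.

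For the patient in 13.1.2, the imputed stop would then be no later than 31 December of the recorded year, and the 3.0 to 13.9 months beyond it would no longer count as migalastat time. The cost is a few sentences in the SAP and minor programming. No new data are needed.
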